Title	Can High-Intensity Interval Training (HIIT) reduce the risk of diabetes relapse following discharge from the NHS Path to Remission Programme? – a pilot study
Short title	HIIT post LCD
Chief Investigator	[name]
Objectives	To determine the effect of a 16-week home-based HIIT intervention on markers of glucose metabolism and glycaemic control in individuals with T2D that have achieved diabetes remission in the NHS Path to Remission Programme.
Trial Configuration	Parallel group, non-blinded, randomised control study
Setting	Clinical research facility (Postgraduate Centre, University of Nottingham, Derby Campus)
Sample size estimate	This is a pilot study, therefore no power calculation has been performed
Number of participants	20 participants will be recruited and allocated 1:1 into intervention or control groups
Eligibility criteria	
 • Adults between the age of 18-70 years • Ability to provide informed consent. • Completed the NHS Path to Remission programme and achieved diabetes remission (HbA1c <48mmol/mol (6.5%), and off diabetes medications for at least three months)
Description of interventions	The intervention group will participate in a 16-week HIIT programme involving 3 sessions per week in their own homes. The HIIT sessions are comprised of five 1-minute intervals of body-weight exercises interspersed with 90-second active recovery periods. The control group will continue with their usual levels of activity.
Duration of study	
Each participant will be involved in the study for 16 weeks.
 
The study is expected to commence in November 2024 and be completed by the end of August 2026.

Randomisation and blinding	Participants will be randomised to the two groups using the “sealed envelope” online software. Research staff in direct contact with participants will not be blinded, however staff involved solely in analysis of samples and data will be blinded to the randomisation of participants.
Outcome measures	
The primary endpoint for this study will be beta-cell function assessed during an intravenous glucose tolerance test (IVGTT)
 
Secondary outcome measures include:
 
 • Insulin sensitivity • Overall glycaemic control • Body weight • Body composition • Skeletal muscle function

	
 • Skeletal muscle structure • Cardiorespiratory fitness (measured as VO_{2max} during cardiopulmonary exercise testing, CPET)

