Upon completion of the IVGTT, participants will be escorted to a different laboratory containing bespoke equipment for muscle function assessment. Initially electromyography (EMG) of the right leg muscles will be performed at various contraction intensities. Next, they will undergo 1 repetition maximum strength testing of left knee extension. Finally, they will undergo a supervised CPET session to determine their VO_{2max} and aerobic threshold (AT). This will be performed on a cycle ergometer with continuous cardiopulmonary monitoring, as is standard practice within our research group (Boereboom *et al.*, 2016; Blackwell *et al.*, 2017). The CPET usually lasts between 8-15 minutes and is followed by a period of monitored recovery for up to 5 minutes. Before leaving, participants will be provided with a light lunch. It is expected that this study visit will last approximately 4 hours so should be completed before 1230. The schematic below provides a visual representation of the study visit.

Intervention Period

Following the first study day, participants randomised into the intervention group will enter the intervention period. These participants will be instructed to perform a HIIT protocol at home 3 times a week for 16 weeks. There will be some flexibility over the distribution of exercise sessions each week but they will be asked not to complete the 3 sessions on consecutive days.

Each session will begin with 2 minutes of jogging on-the-spot as a warm-up. Then participants will perform 5 intervals of exercises at a high intensity for 60 seconds. Each interval will be interspersed with 90 seconds of “active” recovery, involving walking on the spot. The 5 intervals will consist of the following exercises in this order:

1. Star jumps
2. Standing squats
3. On-the-spot sprints
4. Standing squats
5. Star jumps

This pyramid design has been chosen as it can be used to provide participants with a target of repetitions to achieve in the 4th and 5th interval (using the number of repetitions achieved in the 1st and 2nd).

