The control group will not be participating in any exercise intervention. Participants in this group will be instructed to make no significant changes to their current levels of physical activity for the 16-week period.

All participants will be advised to continue their regular medications as prescribed. These regular medications will have been recorded at the screening appointment and documented in the CRF.

Final Visit

At the end of the 16 weeks (approximately 72 hours after their final HIIT session), all participants will undergo their final study visit. This will follow the exact same format of the first study visit, except at the end of this study visit participants will be asked to complete a feedback questionnaire, thanked for their involvement and exited from the study. Subsequently, their General Practitioner will be sent a letter detailing their results with a copy also sent directly to them. If participants have any questions regarding their results and ongoing management, they will be advised to discuss these with their General Practitioner.

Compliance

Participants in the intervention group will be asked to complete an exercise documentation pack, in which they will be required to record details of each exercise session performed. They will be contacted by phone (or email) at regular intervals (at least weekly) and compliance will be one of the issues discussed, with reference to their documentation pack.

Participants will be expected to perform the HIIT sessions 3 times per week. However, this can be increased to 4 times if a session has been missed from the previous week. Compliance will be deemed acceptable if >80% of sessions are performed. Participants will be excluded if they:

- are unable to complete 4 or more consecutive sessions
- miss more than 7 sessions in total
- fail to complete the set exercise regime in 7 or more sessions

The number of participants excluded due to poor compliance will be recorded and reported in the study report and any potential publications.

Criteria for terminating trial

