Two-way analysis of variance (ANOVA) will be used to determine statistically significant differences between the mean baseline and follow-up measurements of all outcomes in both groups. Additionally, the independent samples t-test will be used to compare mean changes in outcomes between the two groups and test for statistical significant differences between them. Non-parametric alternatives will be used if data are non-normally distributed. If, despite randomisation, the mean value of an outcome at baseline is different between the groups then linear regression analysis will be performed to account for the baseline difference. The significance level will be set at $p=0.05$.

Interim analysis of available data will be performed 8-10 months into the course of the study, in order to inform the funding organisation that progress is being made. Finally, in order to maintain the safety of participants, the occurrence of adverse events will be continuously monitored and if an unacceptably high incidence of such events is noted, this will be highlighted to the Chief Investigator and Co-Investigators. At this point, a decision will be made regarding continuation of the study, or if other safety procedures are required to reduce the AE occurrence rate.

Sample size and justification

This is a pilot study, as such, no power calculation has been performed to justify sample size. However, a previous study with similar participant numbers has successfully demonstrated significant improvements in beta-cell function following a HIIT intervention (Madsen *et al.*, 2015b).

Assessment of efficacy

The primary endpoint for this study is pancreatic beta-cell function assessed during an IVGTT. Thus, the HIIT intervention will be deemed efficacious if participants in the intervention group have a significantly higher beta-cell function than those in the control group, i.e. there is a greater improvement in insulin response to intravenous glucose after the 16-week intervention than after 16 weeks of usual care. Significant difference will be determined using two-way ANOVA (or other more appropriate statistical tests) as outlined above.

The secondary endpoints will provide evidence of the efficacy of the HIIT intervention on inducing improvements in other measures of cardiometabolic health and are listed below:

- Improvement in insulin sensitivity suggested by increased insulin sensitivity index (derived from the IVGTT) and reduced HOMA2-IR

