With these measures in place, we will endeavour to ensure that less than 10% of the data set will be missing. If this is achieved, the data will be analysed using standard statistical techniques as described above. However, if despite these measures there is greater than 10% missing data, this will be discussed directly with the support statistician and the procedure for dealing with this will then depend on the extent of data that is missing. Techniques such as imputation will be considered if required, however if analysis can be performed without the need for such techniques then this would be the preferred option.

If it is not possible to perform an IVGTT in a particular participant (e.g. due to difficulty obtaining vascular access), no data regarding the primary outcome will be collected for that participant. In this situation, data will still be collected for the remaining secondary outcomes during the first visit. Moreover, the participant will be permitted to participate in the 16-week intervention (or control) period and the second visit will be conducted, however without the repeat IVGTT. In order to ensure the target number of participants is reached, with regard to the primary outcome, an additional participant will be recruited for every participant that cannot complete the IVGTT.

Definition of populations analysed

Full Analysis set: All randomised participants, who participated in at least one HIIT session and for whom at least one post-baseline assessment of beta-cell function is available.

Per protocol set: All participants in the Full Analysis set who are deemed to have no major protocol violations that could interfere with the objectives of the study.

ADVERSE EVENTS

Definitions

An adverse event is any unfavourable and unintended sign, symptom, syndrome or illness that develops or worsens during the period of observation in the study.

An AE does include a / an:

1. exacerbation of a pre-existing illness.
2. increase in frequency or intensity of a pre-existing episodic event or condition.
3. condition detected or diagnosed after medicinal product administration even though it may have been present prior to the start of the study.
4. continuous persistent disease or symptoms present at baseline that worsen following the start of the study.

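### The Full Analysis Set requires at least one HIIT session without limiting this to the HIIT arm, so read literally neither defined analysis set contains any controls

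*Protocol*

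**What the plan says.** Under STATISTICS, Definition of populations analysed, the protocol defines two analysis sets and no others.

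- The Full Analysis Set is made up as follows: "All randomised participants, who participated in at least one HIIT session and for whom at least one post-baseline assessment of beta-cell function is available".
- The second set, called Per protocol, is nested in the first. It keeps only those members judged to be free of major violations.

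The design and the planned comparison are described elsewhere in the protocol:

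- Synopsis: "20 participants will be recruited and allocated 1:1 into intervention or control groups".
- Intervention Period, for those allocated to HIIT: "These participants will be instructed to perform a HIIT protocol at home 3 times a week for 16 weeks".
- Intervention Period, for the others: "The control group will not be participating in any exercise intervention".
- Assessment of efficacy: "the HIIT intervention will be deemed efficacious if participants in the intervention group have a significantly higher beta-cell function than those in the control group".
- Statistics, Methods: "the independent samples t-test will be used to compare mean changes in outcomes between the two groups", in addition to a two-way ANOVA.

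Under Procedures for missing, unused and spurious data, a participant in whom the IVGTT cannot be done stays in the study. For that person "data will still be collected for the remaining secondary outcomes during the first visit", a second visit takes place without the test, and one further participant is recruited.

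The Compliance section and the section on removal and withdrawal provide for taking intervention participants out of the study when they fall short of minimum compliance.

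**The concern.** The two conditions for the Full Analysis Set are joined by *and*, and neither is restricted to one arm. The first can be met only by people who do the intervention. A control who follows the protocol can never meet it. Because the Per protocol set is drawn from the Full Analysis Set, it inherits the gap.

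The primary objective is a comparison of two randomised groups. If the analysis sets are applied as written, one of those groups is empty. If the analyst repairs the rule informally by applying it to the HIIT arm alone, membership of the main analysis set depends on behaviour after randomisation in one arm and not in the other. Which repair to make should not be left to interpretation once data exist. Staff in contact with participants know the allocation, and an interim analysis is planned 8 to 10 months into the study.

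This is not a detail that a separate analysis plan could be expected to supply. The protocol states the rule, and the rule conflicts with the protocol's own comparison.

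**Working it through.** The protocol gives no power or sample-size calculation, so there is no stated figure to reproduce. The check applies the set definitions as filters to the planned numbers.

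**Inputs**

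- Planned total 20, allocated 1:1 (Synopsis): 20 / 2 = 10 per arm.
- HIIT sessions planned per intervention participant (Intervention Period): 3 per week × 16 weeks = 48.
- HIIT sessions per control (Intervention Period): 0 by design.

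**Step 1. The definitions as written, with complete follow-up**

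Full Analysis Set = randomised AND sessions ≥ 1 AND at least one beta-cell assessment after baseline. Per protocol set = Full Analysis Set AND no major violation.

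| Set | HIIT | Control |
|---|---|---|
| Randomised | 10 | 10 |
| Full Analysis Set | up to 10 | 0 |
| Per protocol set | at most 10 | 0 |

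With no controls, the control mean does not exist. Neither the t-test on mean change nor the group term of the two-way ANOVA can be computed. Only a before-and-after comparison within the HIIT arm remains, and that does not address the efficacy criterion.

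**Step 2. The session condition removed, or not applied to controls**

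Degrees of freedom for the t-test = n(HIIT) + n(control) − 2. The protocol gives no expected loss, so 0 to 3 missing final IVGTTs per arm is an assumed range, and every HIIT participant counted here is taken to have done at least one session.

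| Missing per arm (assumed) | Sizes as written (HIIT + control) | Sizes after correction | df after correction |
|---|---|---|---|
| 0 | 10 + 0 | 10 + 10 | 18 |
| 1 | 9 + 0 | 9 + 9 | 16 |
| 2 | 8 + 0 | 8 + 8 | 14 |
| 3 | 7 + 0 | 7 + 7 | 12 |

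**Step 3. The condition kept for the HIIT arm only**

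The controls return. Each HIIT participant excluded for doing no session would be 1 / 10 = 10% of that arm, with no matching exclusion among controls. Such a person has missed 48 of 48 sessions. The Compliance section already excludes anyone who misses more than 7, so the session condition would remove few people beyond those whom that rule removes.

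**Step 4. The post-baseline beta-cell condition**

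This one applies to both arms. A participant whose IVGTT could not be done at the first visit has no repeat test at the second, so can never meet it and lies outside both sets. Whether that affects the secondary outcomes depends on which set they are analysed in, and the protocol does not say.

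**The case against.** The strongest reply is that the intention is plain. The objectives, the Methods and the Assessment of efficacy all compare two groups, the protocol never ties a particular analysis to a particular set, and the likeliest explanation is a missing qualifier restricting the session condition to those allocated to HIIT. This stands as a guess about intent. A reader might infer that the trial will be analysed without controls, or that no randomised comparison is possible at all. The documents do not support that, because they clearly plan one. The defect is narrower: the comparison cannot be made in either set that the protocol defines.

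It can also be said that the HIIT-only reading costs little, because someone with no sessions would be removed anyway. That is largely right. The larger one-sided loss comes from the compliance and removal rules, not from the session condition.

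Two further inferences about participants without an IVGTT should be resisted. A reader might conclude that their secondary data will never be analysed. This would follow only if the Full Analysis Set governs the secondary outcomes, which is not stated and may be settled in an analysis plan not shown here. A reader might also put a fixed percentage loss on each failed IVGTT by dividing by the planned 20. That ignores the replacement rule, under which an additional person is recruited and the target number with an IVGTT is still sought.

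**Conclusion.** The point holds as a contradiction in the text. Taken literally, 0 of 10 planned controls qualify for the Full Analysis Set or the Per protocol set, and the primary between-group comparison cannot be carried out in either. This rests only on the 1:1 allocation of 20 participants, on controls doing no HIIT as planned, and on the absence of any exemption for controls elsewhere in the protocol. It needs no assumption about effect size or variability.

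The probable intended reading restores the controls but keeps a post-randomisation exclusion in one arm. Its own effect is probably small, given the existing removal rules. The conflict with the collection of secondary data from participants without an IVGTT is conditional on the Full Analysis Set applying to those outcomes. The definition must be corrected before analysis because the primary comparison depends on it.

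**What to change.** Replace the Full Analysis Set paragraph with wording to this effect: *The Full Analysis Set comprises all randomised participants, analysed in the group to which they were allocated, regardless of the number of HIIT sessions performed. Each outcome is analysed in all participants with data for that outcome. This is the primary analysis set.* Confine any session criterion to the HIIT side of the Per protocol set.

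This is one paragraph of wording. It restores the controls at no operational cost, and it gives participants without an IVGTT a defined place in the secondary analyses.

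It does not by itself deliver a full intention-to-treat analysis, and a reader should not infer that it does. Analysing each outcome in those with data still needs a value after baseline. The Compliance section and the section on removal and withdrawal take non-compliers out of the study, and no section provides for their final assessment. The rewording cannot recover those outcomes. The new definition therefore has to be reconciled with those two sections, and any cost of that step depends on how the sponsor resolves it.

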A paper copy of the blood test results will be sent to the department. These, along with the rest of the screening information will be reviewed by a clinical member of the research team and discussed with the Chief Investigator, who will make the final decision regarding recruitment. Any abnormal results will be discussed with the prospective participant and their General Practitioner will be informed to ensure this is followed-up appropriately. If an individual is deemed to be suitable for recruitment into the study, they will be invited to attend their first study visit and a letter will be sent to their General Practitioner informing them of their involvement. Prior to the first study visit, the confirmed participant will be randomised into one of the following groups:

[figure not shown]
1. Intervention group
2. Control group

First study visit

The procedure for the first study visit will be identical for all participants, regardless of the group they have been randomised to. Participants will be asked to arrive at the clinical research facility between 0830 to 0900, after fasting from midnight the night before (water will be allowed). Upon arrival, they will have their body weight measured and BIA performed to provide an accurate measure of body composition.

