After the fifth interval exercise, the session will end with another 2 minutes of light on-the-spot jogging. The entire HIIT protocol will last 15 minutes in total. Participants will be provided with a pulse oximeter to take home with them for monitoring of their heart rate and instructed to aim to achieve >85% of their maximum heart rate (HR_{max} – determined from the CPET on the first study day) during each session to ensure they are achieving the desired intensity. They will also receive an exercise documentation pack, in which they will be instructed to document the date and time of every exercise session, the maximum heart rate achieved during the session and any potential problems encountered.

To maintain the safety of participants during the intervention period, a number of measures will be put in place. It will be stressed to participants that if they were to develop any concerning symptoms during the HIIT sessions, they must seek immediate medical attention, either from emergency services, or their General Practitioner. We will ask participants to maintain particular awareness of the following symptoms:

- Chest pain or tightness,
- Palpitations,

- Faintness,
- Sudden pallor,
- Loss of co-ordination,
- Confusion,
- Dizziness, or
- Excessive breathlessness

These symptoms will be detailed in the exercise documentation pack so participants can refer to them during the exercise session. It will also be suggested to participants that they have another person in the near vicinity when performing the sessions (particularly the initial sessions), to ensure someone is immediately present to help obtain medical attention if required.

In addition, participants will be contacted regularly by phone, text or email throughout the intervention period by a member of the research team to discuss any problems, ensure their safety, assess compliance with the programme and obtain consent to continue. Participants in the intervention group will be contacted at least weekly for the first 4 weeks, then at least every two weeks thereafter. The control group will be contacted every two weeks. Participants will also be given a study-dedicated mobile phone number, on which they can contact a member of the research team if they have any queries or concerns that are directly related to their participation in the study.

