Adverse events most associated with HIIT interventions are musculoskeletal injuries and exacerbation/precipitation of cardiovascular disease (such as angina and acute coronary syndrome). However, meta-analyses of HIIT interventions have repeatedly reported a very low incidence of such adverse events, including in people with T2D (Rognmo *et al.*, 2012; Weston, Wisløff and Coombes, 2014; Cassidy *et al.*, 2017; Hannan *et al.*, 2018). Despite this, investigators will remain vigilant for any signs or symptoms suggesting development of these conditions. In addition, participants will be made aware of associated symptoms and will be instructed to seek medical attention immediately if they were to develop.

An AE does not include a / an:

1. medical or surgical procedure (e.g., surgery, endoscopy, tooth extraction, transfusion); but the condition that lead to the procedure may be an AE.
2. pre-existing disease or conditions present or detected at the start of the study that did not worsen.
3. situations where an untoward medical occurrence has not occurred (e.g., hospitalisations for cosmetic elective surgery, social and / or convenience admissions).
4. disease or disorder being studied or sign or symptom associated with the disease or disorder unless more severe than expected for the participant's condition.
5. overdose of concurrent medication without any signs or symptoms.

A Serious Adverse Event (SAE) is any adverse event occurring following study mandated procedures, having received the intervention, that results in any of the following outcomes:

1. Death
2. A life-threatening adverse event
3. Inpatient hospitalisation or prolongation of existing hospitalisation
4. A disability / incapacity
5. A congenital anomaly in the offspring of a participant

Important medical events that may not result in death, be life-threatening, or require hospitalisation may be considered a serious adverse event when, based upon appropriate medical judgment, they may jeopardize the patient or participant and may require medical or surgical intervention to prevent one of the outcomes listed in this definition. In relation to this

specific study, an example would be fracture of a bone directly occurring as a result of performing the HIIT training sessions.

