In the event of a pregnancy occurring in a study participant, the participant will be removed from the study as soon as the research team is made aware. Given the nature of the intervention, it is highly unlikely that the involvement in the study will have any effect on the progress of the pregnancy.

All treatment related serious adverse events will be recorded in the trial master file and adverse events database. Unexpected serious adverse events will be reported within the timeframes to the REC as stated below. The Chief Investigator shall be responsible for all adverse event reporting.

Intervention Related SAEs

A serious adverse event that is unexpected in its severity and seriousness and deemed directly related to or suspected to be related to the study intervention shall be reported to the ethics committee that gave a favourable opinion as stated below.

The event shall be reported immediately upon knowledge of its occurrence to the Chief Investigator.

The Chief Investigator will:

- Assess the event for seriousness, expectedness and relatedness to the study intervention.
- Take appropriate medical action, which may include halting the trial.
- If the event is deemed related to the study intervention, inform the REC using the reporting form found on the NRES web page within 7 days of knowledge of the event.
- Within a further eight days, send any follow-up information and reports to the REC.
- Make any amendments as required to the study protocol and inform the REC as required

Participant removal from the study due to adverse events

Any participant who experiences an adverse event may be withdrawn from the study at the discretion of the research team, with final agreement from the Chief Investigator.

ETHICAL AND REGULATORY ASPECTS

ETHICS COMMITTEE AND REGULATORY APPROVALS

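### Read literally, the SAE definition excludes control-arm and pre-training events, and the REC reporting rule omits serious complications of the study procedures

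*Protocol*

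**What the plan says.** Under Adverse Events, Definitions, the protocol describes an SAE as "any adverse event occurring following study mandated procedures, having received the intervention, that results in any of the following outcomes", followed by the usual list of outcomes.

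The treatment sections say who receives the intervention and when:

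- Controls: "The control group will not be participating in any exercise intervention".
- HIIT arm: "Following the first study day, participants randomised into the intervention group will enter the intervention period".
- Both arms at the first visit, where the IVGTT, strength testing and CPET are done: "The procedure for the first study visit will be identical for all participants, regardless of the group they have been randomised to". The final visit repeats the same format for everyone.

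The Causality section has four grades, each expressed in relation to the study intervention. Under Reporting of adverse events, the recording sentence for serious events reads "All treatment related serious adverse events will be recorded in the trial master file and adverse events database". The next sentence sends unexpected serious events to the REC by the route set out below it. That route, under Intervention Related SAEs, says "If the event is deemed related to the study intervention, inform the REC".

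Two other places bear on the point. The section on maintaining randomisation codes provides for looking up a participant's allocated group when an SAE occurs. The Trial/Study Management section says there will be no Data Monitoring Committee.

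**The concern.** The SAE definition sets two conditions: the event follows study procedures, and the person has received the intervention. Half the trial can never meet the second condition. The other half cannot meet it at the baseline visit, which includes an intravenous glucose bolus and an exercise test to VO2max. The relatedness test then looks only at the intervention, so an event caused by a research procedure counts as unrelated for notification.

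The protocol itself treats these procedures as carrying risk. It lists hypersensitivity and venous thrombosis among the known, very rare, side effects of intravenous glucose. It also sets out ECG, blood pressure, heart rate and oxygen saturation signs to watch for during CPET. With no Data Monitoring Committee, REC reporting is the main external safety check, and as worded it does not reach serious harm from the procedures.

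**Working it through.** The protocol states no figure on this point, so there is nothing to reproduce. The check sets the passages side by side and counts visits.

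**Inputs**

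- Synopsis: 20 participants, allocated 1:1, so 20 / 2 = 10 per arm.
- Treatment and regimen: each participant has an IVGTT and CPET at the first and final visits, so 20 × 2 = 40 planned visits.
- Control section: no exercise intervention at any time.
- Intervention Period: HIIT begins after the first study day.

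**Step 1: the definition.** For each visit, ask whether the participant has received HIIT by then.

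| Visit | Arm | Visits | HIIT received? | Can an event there be an SAE as worded? |
|---|---|---|---|---|
| First | HIIT | 10 | No | No |
| First | Control | 10 | No | No |
| Final | HIIT | 10 | Yes | Yes |
| Final | Control | 10 | No | No |

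Outside the definition: 10 + 10 + 10 = 30 of 40, or 75%. In people rather than visits, 10 of 20 participants can never have an SAE under this wording.

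**Step 2: relatedness and REC reporting.** Take a serious complication caused by the IVGTT, CPET or strength testing itself at the HIIT-arm final visit, the one row where the definition is met. The causality grades ask about the study intervention. An event with another plausible explanation falls in the lowest grade, which counts as unrelated for notification. The REC step applies only to events related, or suspected to be related, to the intervention. So these 10 visits pass Step 1 but have no stated REC route for a procedure-caused event, and the other 30 fail at both steps.

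**Step 3: internal consistency.** Looking up the allocated group after an SAE makes sense only if an SAE can occur in either arm. The definition, taken literally, allows it in one arm only. The two passages cannot both stand.

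**Step 4: what is still captured.** The adverse event definition covers the whole period of observation with no limit by arm. All adverse events are recorded and assessed for seriousness, expectedness and causality, and the Chief Investigator is told of them immediately. The Assessment of safety section adds the case report form, the trial master file and a dedicated database. The exclusion in Steps 1 and 2 therefore affects the SAE label and the REC route, not capture.

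**The case against.** The strongest reply is that the literal reading is not the intended one. The definition itself names study procedures. The Informed consent section uses the word interventions broadly enough to take in examination and history taking. The Causality section also leaves prompt reporting to medical and scientific judgement. This makes a wider reading possible but does not secure it. The Stopping rules section names interventions and procedures separately, the SAE definition states both as conditions, and its study-specific example is a fracture during HIIT. A reporting rule should not depend on staff reading past its words.

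A second reply is that control events are bound to miss an intervention-related route, since HIIT cannot have caused them. That is right for relatedness to HIIT. It does not answer the case of a control harmed by the IVGTT or CPET.

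A reader might also infer more than the documents support:

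- *Serious events would go unseen.* They would not, as Step 4 of the working shows.
- *The termination criterion lacks a control rate.* It is written in terms of adverse events, which are collected in both arms, and it is not framed as a between-arm comparison.
- *Adverse event counts would be biased because the arms are contacted unequally.* The protocol plans no between-arm analysis of adverse events and declares no safety endpoints. The HIIT-arm schedules are minimums: 4 + 12/2 = 10 contacts under Intervention Period and 16 under Compliance, against 16/2 = 8 for controls. Weekly contact satisfies both HIIT-arm statements, so their difference is a minor matter of wording.

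**Conclusion.** The concern holds as a wrongly drawn rule in SAE classification and REC reporting. As worded, 10 of 20 participants can never have an SAE, and events at 30 of 40 planned IVGTT/CPET visits fall outside the definition. A serious event caused by a study procedure has no stated REC route at any of the 40.

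The visit count assumes full recruitment at 1:1, both visits completed by everyone, and an event that arises at the visit itself. Drop-out, or the extra recruits allowed when an IVGTT cannot be done, would change the numbers but not the conclusion. The finding rests on the literal reading; under the looser reading it is an ambiguity that still needs settling. It does not touch the efficacy analysis, and it does not show that adverse events go uncollected. It should be corrected, because the amendment is cheap and external safety oversight is otherwise thin.

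**What to change.** Reconcile the SAE definition, the Causality section, the two reporting sections and the passage on randomisation codes as follows:

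1. Define an SAE as any adverse event meeting one of the listed outcomes, in any participant in either arm, from consent to the final visit. Remove the condition of having received the intervention.
2. Grade causality against the intervention or any study procedure, naming the IVGTT, CPET and strength testing, and record which one is suspected.
3. Use that same relatedness test to trigger REC reporting.
4. Amend the recording sentence so that all SAEs, related or not, are entered as SAEs in the trial master file and the adverse events database.

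As a minor tidy-up, make the HIIT-arm contact frequency the same under Intervention Period and Compliance.

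The cost is a protocol wording amendment, matching changes to the adverse event form, and slightly more reporting. No visit, sample or analysis changes.
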